#### **7.4 Evaluation of response**

All patients included in the study must be assessed for response to treatment, even if there are major protocol treatment deviations or if they are ineligible. Each patient will be assigned one of the following RECIST categories: 1) complete response, 2) partial response, 3) stable disease, 4) progressive disease, 5) early death from malignant disease, 6) early death from toxicity, 7) early death because of other cause, or 9) unknown (not assessable, insufficient data). [Note: By arbitrary convention, category 9 usually designates the "unknown" status of any type of data in a clinical database.]

All of the patients who met the eligibility criteria (with the possible exception of those who received no study drug) should be included in the main analysis of the response rate. Patients in response categories 4-9 should be considered to have a treatment failure (disease progression). Thus, an incorrect treatment schedule or drug administration does not result in exclusion from the analysis of the response rate. Precise definitions for categories 4-9 will be protocol specific.

All conclusions should be based on all eligible patients. Subanalyses may then be performed on the basis of a subset of patients, excluding those for whom major protocol deviations have been identified (e.g., early death due to other reasons, early discontinuation of treatment, major protocol violations, etc.). However, these subanalyses may not serve as the basis for drawing conclusions concerning treatment efficacy, and the reasons for excluding patients from the analysis should be clearly reported.

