### **1.2 Exploratory Aims:**

- 1.2.a Test FMISO HCC tumor uptake and blood flow as independent predictors of patient outcome prior to TACE.
- 1.2.b Test FMISO post combination treatment HCC tumor uptake and blood flow as predictors of response in of patients receiving TACE+ stereotactic hepatic radiation therapy.

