### 3. PATIENT SELECTION

#### 3.1 Eligibility Criteria

3.1.1 Adult ( $\geq 18$  years of age) patients with documented HCC tumor mass  $\geq 3$ cm, who are scheduled to undergo TACE with additional SIRT

3.1.2 The appropriate criteria for inclusion for this patient population are:

3.1.2.a Biopsy or radiological diagnosis of HCC (defined as Organ Procurement and Transplantation Network (OPTN\*) Category 5 lesion either on CT or MRI)

3.1.2.b. Scheduled for TACE (using doxorubicin-eluting beads) + SBRT

3.1.2.c. Willingness to undergo PET/CT

3.1.2.d. Able to lie on the imaging table for up to 1 hour.

3.1.2.e. Able to provide signed informed consent.

3.1.2.f. Women with childbearing potential must have a negative urine  $\beta$ -hCG test day of procedure

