## 6.a. General Definitions (from 21 CFR 312.32 (a))

**Adverse Event (AE):** An **Adverse Event** is an untoward medical occurrence associated with the use of the drug in humans, whether or not considered drug related. For this study, the drug is FMISO and adverse events would include any events experienced by a study participant during the Adverse Event reporting period defined in **Table 3**, whether or not it was considered to be related to the FMISO. At the conclusion of the imaging study, the imaging technologist will observe the patient and also inquire if they are back to their usual state of health. If a negative answer is received, then the physician will be called to investigate this report as a possible adverse reaction.

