**Investigational Agent:** An investigational agent is any agent held under an Investigational New Drug (IND) application. For purposes of this study, FMISO is the investigational agent.

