## **7. STATISTICAL CONSIDERATIONS**

### **7.1 Study Design/Endpoints**

This is a Phase II study of a PET imaging agent, [F]FMISO, in patients with HCC who will be receiving standard care with TACE, and with radiation. The imaging study will not impact the patient's treatment. The objective of this study is to evaluate the potential of [F]FMISO as a non-invasive indicator of tissue hypoxia in HCC patients to provide tumor imaging data.

The primary endpoint is changes in [F]FMISO parameters (HV and T:Bmax) between baseline and follow-up scans. The regional tissue: blood values will be determined and hypoxic volume of the primary tumor and metastases will be calculated. The number of pixels in the tumor volume with a T/B ratio  $\geq 1.2$ , indicating significant hypoxia, will be determined and converted to milliliter units to measure the HV. In each tumor region, we will also locate the pixel with the maximum T/B ratio and include this variable, T/Bmax, in our analysis. HV evaluates the volume of tumor that has crossed the threshold for hypoxia and T/Bmax depicts the magnitude of hypoxia.

The exploratory endpoints include overall survival (OS), disease free survival (DFS) and response to XRT by RECIST, mRECIST or EASL (because enhancement changes are known to better reflect treatment response than size changes) criteria.

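### The response analysis set in section 7.4 turns on receipt of study drug, which here is the FMISO tracer, so patients never given radiotherapy can be scored for response to it

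*Combined protocol and SAP*

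**What the plan says.** Section 7.4 (Evaluation of response) sets the rule for its main response-rate analysis, which begins: "All of the patients who met the eligibility criteria (with the possible exception of those who received no study drug) should be included in". It scores categories 4 to 9 as treatment failure, and category 9 is unknown or not assessable. It does not accept a wrong treatment schedule as a reason for exclusion, and it rests every conclusion on the full eligible set. Subanalyses that drop patients with major deviations are allowed but may not support conclusions about treatment efficacy.

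Other sections fix what the drug is and who is eligible:

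- Section 6.a: "For this study, the drug is FMISO". Its definition of investigational agent adds: "For purposes of this study, FMISO is the investigational agent".
- Section 7.1 describes the study as one "in patients with HCC who will be receiving standard care with TACE, and with radiation", and says the imaging does not affect treatment.
- Section 3.1, item 3.1.2.b, requires only that the patient be "Scheduled for TACE (using doxorubicin-eluting beads) + SBRT".
- The Figure 1 caption puts PET #1 before treatment, PET #2 one month after the last TACE and before SBRT, and PET #3 one month after SBRT ends.

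The response questions concern treated patients. Section 7.1 lists "response to XRT by RECIST, mRECIST or EASL" among the exploratory endpoints. Aim 1.2.b tests uptake and blood flow after combination treatment "as predictors of response in of patients receiving TACE+ stereotactic hepatic radiation therapy". Section 7.3 fits logistic models of response (yes or no) to the baseline scan, the follow-up scans and the changes one at a time, and adds an ROC cut point if an association is found.

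**The concern.** The inclusion rule suits a trial in which the study drug is the therapy. There, excusing patients who took none of it removes those who could not have responded to it. Here the same words excuse only patients who never had the tracer, and the tracer comes first. A patient who has PET #1 and then receives neither TACE nor SBRT, or TACE without SBRT, has received study drug and is kept.

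For response to radiation, such a patient carries no information whichever way the outcome is coded. Coded as failure, the patient lowers the response rate. If the patient responded to TACE alone and is coded as a success, the response is credited to radiation that was never given. The same outcome enters the baseline-scan and post-TACE-scan logistic models and the ROC analysis. If patients who miss treatment differ in FMISO uptake from those who receive it, the estimated link between uptake and response is distorted. With 20 patients, a few such cases matter.

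**Working it through.** **No figure in the plan to reproduce.** The plan gives no expected response rate and no rate of patients not treated. Its sample-size figures in section 7.2 concern uptake and paired change in T/Bmax, and neither depends on the response set.

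**Who enters what.** This combines 7.4 with the scan timing in Figure 1 and the models in 7.3.

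| Patient | Scans as timed | In the 7.4 response rate? | Response models entered |
|---|---|---|---|
| Scanned, no TACE, no SBRT | #1 | Yes | Baseline |
| TACE, no SBRT | #1, #2 | Yes | Baseline, post-TACE, change from #1 to #2 |
| TACE and SBRT | #1, #2, #3 | Yes | All |

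The first two rows cannot have a response to radiation, yet both count towards it. Neither enters a model that needs PET #3. That model therefore cannot satisfy the 7.4 sentence resting every conclusion on all eligible patients once one eligible patient misses SBRT.

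**Effect on the response rate.** Inputs: N = 20 (section 7.2). Assumptions, because the documents give neither: u = 1 to 5 patients untreated, and response p = 40% to 60% in the treated. If all u are scored as failures,

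observed rate = p × (20 − u)/20, so the loss is p × u/20.

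| u | p = 40% | p = 60% |
|---|---|---|
| 1 | 0.40 × 1/20 = 2 points | 0.60 × 1/20 = 3 points |
| 2 | 4 points | 6 points |
| 5 | 10 points | 15 points |

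With whole patients: 9 responders among 18 treated is 50.0% (Clopper-Pearson 95% CI 26.0% to 74.0%). The same 9 among 20 eligible is 45.0% (23.1% to 68.5%).

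**Effect on the FMISO-response association.** Assume 60% response in the treated, unrelated to hypoxic volume (HV), with patients split 10 and 10 at the median HV. Let k untreated patients, all scored as failures, lie in the upper half and none in the lower. Response is then 0.60 below the median and 0.60 × (10 − k)/10 above it.

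- k = 4: 0.36 above the median. Odds ratio (lower half to upper half) = (0.60/0.40)/(0.36/0.64) = 2.67.
- k = 2: 0.48 above the median. Odds ratio = (0.60/0.40)/(0.48/0.52) = 1.63.
- Four untreated, two in each half: 0.48 in both halves. Odds ratio = 1.

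The first two are worst cases. If missing treatment were unrelated to HV, the chance that all four fall in the upper half is C(10,4)/C(20,4) = 210/4,845 = 4.3%.

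**The case against.** Several points on the other side stand and limit the finding.

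- **Aim 1.2.b.** A reader might infer that the untreated contaminate the model for this aim. They do not. Its predictor is the scan after combination treatment, and a patient without SBRT has no PET #3. What remains is the conflict with the all-eligible sentence.
- **The bar on subanalyses.** A reader might infer that 7.4 forbids any conclusion from the treated subset. That bar is limited to treatment efficacy, whereas aim 1.2.b is about prediction. The separate sentence on all conclusions is broader and does create the tension.
- **Untreated means failed.** Not always. A TACE-only patient may respond to TACE. Stable disease (category 3) is outside the failure list, and 7.3 does not define response yes or no.
- **The odds ratios.** They need every untreated patient to be a non-responder in the upper HV half. The documents report no link between HV and missing treatment. Section 2.2.d says hypoxic tissue did not correlate with tumor volume in earlier studies, although section 2.1.a says hypoxic volume can rise as a tumor grows. In the k = 4 case, an approximate Wald 95% CI runs from 0.4 to 16, so 20 patients could not establish such an effect anyway.
- **Restricting to treated patients has a price.** Reaching SBRT is a post-baseline event. Applied to the baseline scan and outcome (aim 1.2.a), the restriction could drop patients who worsened after TACE and hide a real association.

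It can also be said that 7.4 makes its exception only a possibility, that it never defines study drug, and that 7.3 does not expressly tie its models to the 7.4 set. These do not rescue the text. If study drug was meant as the TACE drug, that contradicts 6.a, and no section supplies a treated-patient response set.

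**Conclusion.** The concern holds in limited form. As written, 7.4 keeps patients who were scanned but not irradiated in the main response analysis and lets them be scored for response to radiation. The response rate is affected, as are the logistic and ROC analyses of response based on the baseline or post-TACE scan. The PET #3 model is not contaminated, but it is at odds with the sentence on all conclusions.

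The size cannot be known from the documents. Under the assumed ranges, the loss in response rate is 2 to 15 percentage points if every untreated patient is scored as a failure, and smaller if some respond to TACE. Bias in the odds ratio arises only if missing treatment is related to FMISO uptake; 1.6 to 2.7 are worst cases, not expectations.

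Response is an exploratory endpoint. The primary analysis of change in HV and T/Bmax does not depend on this rule. The correction is worth making because the stated rule gives a wrong answer to the stated question and costs little to change.

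**What to change.** In section 7.4:

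1. Replace the exception for patients without study drug with sets defined by treatment received. For response to TACE, use eligible patients who received at least one TACE. For response to XRT and for aim 1.2.b, use those who also started SBRT.
2. Limit the sentence on all conclusions so that it refers to the set named for each analysis.
3. Keep all eligible patients for the analysis of outcome from the baseline scan (aim 1.2.a).
4. Report how many eligible patients did not receive TACE or SBRT, with reasons.
5. Show the all-eligible response result alongside the treated-set result.

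The cost is a rewording, with no new data and no change to patient care. The XRT-response set becomes slightly smaller and is selected on having reached SBRT. Items 4 and 5 make that selection visible.
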